terms of specific educational practices. All emphasize education of parents and patients so that decisions are made in an informed manner. All sites share an emphasis on activating parents and patients as active consumers of health care who participate in the planning of their treatments. Consideration of CSII or CGM may be initiated either by the parent, adolescent or HCP, and typically the candidacy moves forward only for patients deemed to have sufficient self-management skill and responsibility. In general, decisions such as CSII or CGM are made over a course of several clinic visits and rarely made at the same clinic visit at which the idea is raised initially for consideration. The experiences of each UCP participant will be carefully characterized in terms of content, duration, frequency, youth involvement, and participation of significant others so that this practice variability can be described accurately and, where possible, appropriate secondary statistical analyses performed. At the first study visit after their decisions are made, each youth-parent dyad will be asked to reconstruct precisely the types and sources of information they used, the duration of their decision-making process, the degree to which others were involved in the decision making process and the relative influence of each of these experiences in affecting their eventual decision. (See Appendix)

SMDM Intervention: All of the above features of Usual Clinical Practice will be augmented by:

- Orientation to optimal use of the decision aid web platforms by research staff
- Use of IPDAS-compliant decision aids on web platform by adolescent and parent (plus others per family preference)
- Realistic exposure to benefits and challenges associated with CSII vs. Multiple Daily Injections or with CGM (Conventional finger-stick BG checks with or without addition of CGM)
- Comprehensive understanding of the added treatment burden associated with CSII or CGM
- Exposure to the pertinent evidence base summarized for a lay audience
- Clarification of values and preferences
- Involvement of others per participants' choice
- Exposure to narrative stories of people who faced the same decision
- Preparation of an individualized summary of the patient's SMDM experience and remaining questions by the DE at a follow-up visit once the family has finished using the decision aid
- Return visit with health care provider to discuss the above summary

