Actual schedule of diabetes clinic visits for a given patient deviates substantially from the typical quarterly appointments.	Adolescents will not be followed for more than 12 months. If a clinic visit occurs between 9 and 12 months after the Baseline Visit, the measures designated for collection at Visit 5 will be collected at that visit, regardless of the number of previously completed study visits for that adolescent.
Indecision between adolescent and parent resulting in a period in which no clear decision is made.	Measurement plan will have slightly different measurement schedules for families who clearly decide to accept CSII or CGM, for families who clearly decide to decline CSII or CGM, and for families who either cannot reach a decision or wish to defer decision making until a later date.
Adolescent is considered to be a candidate for both CSII and CGM simultaneously.	Adolescent will be given access to both the CSII and CGM decision aids.
Adolescent already on CSII is a candidate for the so-called "low glucose-suspend" insulin pump.	Adolescent will be given access to both the CSII and CGM decision aids and especially encouraged to review the content related to the closed-loop artificial pancreas.
Adolescent and/or parent want to consider CSII or CGM, but HCP disagrees.	Adolescent is considered ineligible for the study until HCP supports the adolescent's candidacy for CSII or CGM.
Enrolled family does not have a computer for CGM or CSII downloads or for online completion of study questionnaires.	Downloads of devices and completion of questionnaires will be done in the clinic.

Adolescent initiates either CSII or CGM and then later decides to consider adding the other device to the diabetes regimen.	Device downloads will be collected for each device from the time the device is received and initialized. Measures of decision quality and device knowledge will be completed at the next study visit after receipt and initialization of the second device.
-----------------------------------------------------------------------------------------------------------------------------	-------------------------------------------------------------------------------------------------------------------------------------------------------------------------------------------------------------------------------------------------------------

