Description of Decision Making Process: This 10-item measure asks parents and adolescents in the UC Group only to report how often they did certain activities during the decision making process and how it affected their choice, the outcome of the decision making process and how satisfied they are with their decision. This measure was constructed for this study to enable participants randomized to the UCP group to describe the process by which they made a decision about CSII or CGM. If decision making has been actively deferred, that will be treated as a decision having been made. If decision making has simply not occurred, in the absence of a definite statement to defer decision making until some point in the future, this measure will be obtained at Visits 3 and 5. Information yielded from this measure will be used primarily for descriptive purposes to enable readers to place the UCP condition in a concrete perspective.

Measures obtained at Visit 3 and Visit 5

Decision Regret Scale (DRS): The DRS is a 5-item scale for measuring a patient's degree of regret (or satisfaction) after a specific decision.¹⁶³ Items are rated on a 5-point scale ranging from "strongly agree" to "strongly disagree", and higher scores reflect more perceived regret. Internal consistency was .81 in a prior study. The scale will be completed by parents and adolescents in both the SMDM and UCP groups. Administration time is about 2-3 minutes.

SURE Test: The SURE Test is a 4-item screening tool to measure decisional conflict in patients facing clinical decisions in primary care. If the total score is less than 4, the patient is experiencing decisional conflict. The SURE Test will be completed by parents and youth in both groups at Visit 3 and at Visit 5. Administration time is about 2-3 minutes.

Measure obtained at Baseline (Visit 1) and Visit 2

Test of CSII or CGM Knowledge: Each parent and adolescent will complete a 5-item test of CSII or CGM knowledge based on content of the respective decision aids at baseline and at Visit 2 (Or the first visit after the

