Insulin Pump Use Profile/CGM Use Profile (P,C)					
Hypoglycemia Diary (B)					

HbA _{1c} (A)					
Rapid Estimate of Adult/Adolescent Literacy in Med. (B)					
Diabetes Numeracy Test (B)					
Diabetes Self Management Profile-Self Report (B)					
Test of CSII or CGM Knowledge (B)					
Decision Regret Scale (B)					
SURE Test (B)					
Diabetes Technology Questionnaire (B)					
SMDM Satisfaction Scale (B, HCP)					
Description of Decision Making Process (B)					
Decision Aid Utilization Statistics (Monthly Reports)					

*Baseline assessment (0 Months) will occur just prior to randomization to SMDM or UCP. Respondents for each measure are HCP =Adolescent's diabetes health care provider; P = Parent; A= Adolescent; B = Both. All measures are obtained from both the SMDM and UCP groups unless otherwise stated. The Decision Regret Scale, SURE Test and the Description of the Decision Making Process may be repeated at other visits if additional medical decisions (CSII, CGM) are raised for consideration. The Test of CSII or CGM Knowledge will be administered at the first post-decision visit, which is expected to be Visit 2 for most participants. As mentioned above, those who enroll after 3/31/15 are likely to be followed for only 6 months unless PCORI

decides to allow no-cost extensions.

B.5. Statistical Analyses:

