Data Management and Statistical Analysis Plans The primary efficacy endpoints are indices of extent of engagement in CSII (mean number of bolus infusions/day; mean number of uses of "wizard" functions/day) or CGM use (mean number of hours of CGM use/day); and measures of decision quality (Test of CSII or CGM Knowledge; SURE Test; Decision Regret Scale; Diabetes Technology Questionnaire) at each post-decision visit. Secondary efficacy endpoints will include: HbA_{1c} measured quarterly, treatment adherence (DSMP-SR parent and youth) total scores obtained at Visits 1, 3 and 5; and Hypoglycemia Diary obtained at each quarterly clinic visit.

The Full Analysis Set will consist of all participants who provided at least one post baseline assessment record. The Completer Analysis set will include all participants who provided all post baseline primary efficacy assessment results.¹⁶⁶⁻¹¹⁶⁸ Efficacy analyses will be performed on both sets, providing both "Intention to Treat" (Full Analysis Set) and "Per-Protocol" (Completer Analysis Set) analyses. All collected data will be summarized in graphs and tables. Categorical variables will be summarized using frequencies and percentages, while quantitative variables will be described by presenting mean, median, standard deviation (or standard error of mean), minimum and maximum. Data will be summarized by group (SMDM and UCP) and type of medical decision (CSII or CGM) as well as assessment time points. Besides tabular presentation, graphical presentations of some important variables related to primary and secondary endpoints will be provided.

Assumptions for all proposed models will be checked before statistical analyses.¹⁶⁶⁻¹⁶⁸ Appropriate transformations or non-parametric methods will be used in cases of violated model assumptions. For graphical comparison of data that are sufficiently normally distributed, group means and SE of mean will be presented via bar charts. In case of substantial deviation from normality, side by side boxplots will be used for graphical comparisons. Exploratory Subgroup analyses will be conducted as needed. All tests will be performed against a two-sided alternative at the $\alpha = 0.05$ significance level and a 95% confidence interval and/or a p-value will be provided for inferential purposes. Data from all clinics will be pooled for the analyses. All analyses will be performed using the most recent version of the SAS statistical software package.

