Demographic and baseline characteristics (age, race, ethnicity, family composition, marital status, SES), primary and secondary end points, and biochemical, psychological, and behavioral variables will be summarized by intervention groups. One way analysis of variance (ANOVA) of each continuous baseline characteristic and a Fisher exact test/chi-square test/CMH test for each categorical variable will be used to compare the intervention groups at baseline. These comparisons will be used to evaluate the balance of demographic and baseline characteristics among intervention groups. Analyses of primary and secondary end points will be adjusted for significantly imbalanced baseline characteristics. For those measures completed separately by parents and youths, when parent and youth scores are correlated at $r > .70$, a combined parent-adolescent score for that variable will enter analyses. Otherwise, separate analyses will be completed on parent and adolescent scores. A mixed models (or multilevel modeling) approach will be used to test the hypotheses listed below.¹⁶⁹⁻¹⁷² The methods advocated by Holmbeck¹⁷³ will be used to evaluate baseline variables that moderate/predict SMDM-UCP treatment effects on primary study outcomes. Candidate moderator variables will include SES, youth age and gender, race/ethnicity, family structure, and health literacy and numeracy. The methods advocated by Holmbeck¹⁷³ will also be used to evaluate variables that may mediate SMDM-UCP treatment effects on primary study outcomes. In each case, these will include measures that are obtained serially and concurrently with the primary study endpoints. SAS subroutines for addressing the potential confounding influences of time- dependent covariates (e.g. youth age) will be employed as needed in these mediational analyses. With five measurement points for HbA_{1c} and hypoglycemia, the proposed mixed models approach will be capable of detecting longitudinal associations among study variables that are non-linear in form.

Hypothesis 1: Compared to UCP, the SMDM group will have significantly more favorable status in terms of indices of optimal use of CSII or CGM, scores on the CSII or CGM Knowledge Test, SURE Test, Decision Regret Scale, Diabetes Technology Questionnaire and SMDM Satisfaction Scale at each follow-up measurement point.

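### The primary decision-quality endpoints are defined at post-decision visits, against the plan's own fixed schedule; only the Knowledge Test actually runs on a decision clock, and it has no stated post-test for families who never decide

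*Combined protocol and SAP*

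**What the plan says.** B.5 (Data Management and Statistical Analysis Plans) lists, among the primary efficacy endpoints, "measures of decision quality (Test of CSII or CGM Knowledge; SURE Test; Decision Regret Scale; Diabetes Technology Questionnaire) at each post-decision visit". Hypothesis 1, in the same section, instead tests these measures at every follow-up; its list ends "SMDM Satisfaction Scale at each follow-up measurement point".

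B.3 and B.4 set the collection:

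- SURE: "The SURE Test will be completed by parents and youth in both groups at Visit 3 and at Visit 5". No decision is required.
- Decision Regret Scale: listed under "Measures obtained at Visit 3 and Visit 5", for both arms.
- DTQ: Visits 1, 3 and 5, both arms.
- Knowledge: baseline, then "The Test of CSII or CGM Knowledge will be administered at the first post-decision visit, which is expected to be Visit 2 for most participants".

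On the pace of decisions, the account of usual clinical practice (UCP) in B2 says "In general, decisions such as CSII or CGM are made over a course of several clinic visits". The practical-considerations table in B2 promises a separate measurement schedule for "families who either cannot reach a decision or wish to defer decision making until a later date", but B.4 prints one schedule for all. B.3 counts active deferral as a decision, but that rule sits under the Description of Decision Making Process, a form B.3 assigns to the UCP arm. That form has a fallback at Visits 3 and 5 for families who have simply not decided. The Knowledge Test has no such fallback in B.3 or B.4.

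**The concern.** Whether and when a family decides is a post-randomisation event. SMDM acts on it directly: two to four weeks with the decision aid, a meeting with the diabetes educator, then a clinic visit meant to bring the family to a shared decision. If only post-decision visits count, the arms are compared among families selected by something that assignment can change, and randomisation no longer protects the contrast.

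This matters most for SURE, because being unable to decide is close to what SURE measures. SURE has no baseline administration, so an excluded family leaves no earlier score to fall back on. For Knowledge the condition is built into collection, so both the existence of the score and the elapsed time at testing can differ by arm. Two further uses inherit the problem. The Completer set requires every post-baseline primary assessment, so a family without a Knowledge post-test may fail it. Knowledge, SURE and Decision Regret are also the mediators in Hypothesis 3.

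**Working it through.** **Step 1: set the rules side by side.**

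| Measure | Collected (B.3, B.4) | Collection waits for a decision? | B.5 endpoint text | Hypothesis 1 |
|---|---|---|---|---|
| SURE | Visits 3, 5 | No | post-decision visits | all follow-up points |
| DTQ | Visits 1, 3, 5 | No | post-decision visits | all follow-up points |
| Decision Regret | Visits 3, 5 | No, though the scale presupposes a decision | post-decision visits | all follow-up points |
| Knowledge | Baseline, then Visit 2 or the first visit after the decision | Yes | post-decision visits | all follow-up points |

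For SURE and DTQ, data on undecided families exist and the question is whether the analysis uses them. For Knowledge, the data may not exist.

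**Step 2: what the plan quantifies.** It gives no undecided share and no time to decision, overall or by arm. The nearest figure is the power statement: 0.87 for about 0.4 SD with 150 completers, taken here as 75 per arm. Using power = Φ(d√(n/2) − 1.96), 0.4 × √37.5 − 1.96 = 0.49, which gives 0.69 and not 0.87. That mismatch is a separate matter; 0.69 is the starting value below.

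**Step 3: loss of information (assumed shares).** If a fraction u of the 150 is left out because undecided, power at 0.4 SD, two-sided 0.05, is:

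- u = 0: N = 150, power 0.69
- u = 10%: N = 135, power 0.64
- u = 20%: N = 120, power 0.59
- u = 30%: N = 105, power 0.54

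**Step 4: selection shift (assumed shares and gap).** Let decided families score g SD better than undecided ones, with equal overall means in the two arms. The decided mean in an arm is then the overall mean plus u × g, so the decided-only contrast (SMDM − UCP) is (u_SMDM − u_UCP) × g.

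- 10% vs 20%, g = 0.5 to 1.0: −0.05 to −0.10 SD
- 10% vs 30%, g = 0.5 to 1.0: −0.10 to −0.20 SD
- Shares swapped: the same sizes with a positive sign

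Against the 0.4 SD target this is 0.05/0.4 = 12.5% to 0.20/0.4 = 50%.

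**Step 5: SURE illustration (assumed inputs).** Suppose every undecided family scores below 4, and so do 20% of decided families in each arm. The proportion in conflict among all families is u + (1 − u) × 0.20.

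- UCP, u = 25%: 0.25 + 0.75 × 0.20 = 40%
- SMDM, u = 10%: 0.10 + 0.90 × 0.20 = 28%
- All families: a 12-point benefit. Decided only: 20% vs 20%, no difference.
- Shares swapped: 28% (UCP) vs 40% (SMDM), a 12-point harm, also hidden as 20% vs 20%.

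**Step 6: Knowledge timing (assumed inputs).** Suppose 85% of SMDM and 55% of UCP families decide by Visit 2 (month 3) and the rest at months 6 to 9.

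- SMDM: 0.85 × 3 + 0.15 × (6 to 9) = 3.45 to 3.90 months
- UCP: 0.55 × 3 + 0.45 × (6 to 9) = 4.35 to 5.70 months

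The remark in B.3 that mixed models tolerate varying schedules does not settle this. A single follow-up score whose presence and timing may depend on arm is not repaired by the model.

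**The case against.** In the plan's favour, the B.5 phrase can be read as loose shorthand for follow-up visits, since a decision is expected by Visit 2 for most families. SURE, Decision Regret and DTQ are on fixed visits in both arms, Hypothesis 1 is not tied to a decision, and the Full Analysis Set needs only one post-baseline record. All of that stands. A reader might infer that undecided families drop out of SURE, or that the arms are assessed at different times on every measure. The documents do not support either: loss from SURE and DTQ occurs only if the B.5 phrase is applied literally, and only Knowledge timing can shift.

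The direction is also open. One might infer that UCP has more undecided families and that the rule hides a benefit of SMDM. But A.5 lists recognising that a decision can wait as a way SMDM may help, B2 lets the closing SMDM visit end in deferral, and SMDM adds steps to usual practice. The several visits quoted for usual practice run from when the idea is first raised, not from randomisation.

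Testing knowledge once a family has decided is a defensible quantity. The missing schedule for undecided families may sit in the visit checklists that B2 says are held elsewhere, so the fair statement is that B.3 and B.4 give no such post-test, not that none exists.

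What remains is that B.5 contains two analysis rules for the same primary measures, and that the Knowledge score is conditional on deciding.

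**Conclusion.** The point holds as a conflict in endpoint definition plus a decision-triggered Knowledge Test. The B.5 endpoint text disagrees with B.3, B.4 and Hypothesis 1. Left unresolved, the choice between the two rules could be made after the data are seen, and one of them conditions on an event that assignment can affect. For SURE and DTQ the bias is zero if the fixed-visit rule is followed. For Knowledge it arises under the plan as written, to whatever extent the share and timing of decisions differ by arm.

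Neither size nor direction can be read from the documents. The shifts of 0.05 to 0.20 SD, the fall in power from 0.69 to between 0.64 and 0.54, the 12-point SURE example and the timing example all rest on assumed undecided shares and gaps. They show that the effect could matter against a 0.4 SD target, not that it will.

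**What to change.** 1. In B.5, replace the post-decision wording with fixed visits counted from randomisation. Analyse SURE and DTQ at Visits 3 and 5 for all randomised families with data, whatever their decision status, in agreement with B.3, B.4 and Hypothesis 1.
2. Give the Knowledge Test to every family at Visit 2 whether or not they have decided, and make that the primary Knowledge comparison.
3. Keep a decision condition only for the Decision Regret Scale, and state for that purpose, in both arms, whether active deferral counts as a decision.
4. Record decision status and date at each visit. Report the proportion undecided and the time to decision by arm, beside the SURE result.
5. Set out the schedule for undecided families that B2 promises, or delete the promise.

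The cost is wording in B.3 to B.5 and a status field at each visit. No new instrument or visit is needed: Visit 2 is already the expected time of the Knowledge Test for most families, and SURE and DTQ are already collected. The real downside is that some families, possibly more in UCP, take the Knowledge Test before deciding, perhaps before their usual education is complete, on a test built from the decision aids. The endpoint becomes knowledge at about 3 months rather than knowledge once decided, and the plan should say so.

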A Diabetes Educator (DE) at each Nemours site and the Barbara Davis Center will conduct face to face interactions with SMDM participants using the web-formatted decision aid as the framework for delivery of the SMDM intervention. Each patient, parent and any other supportive persons they wish to invite will meet with the DE after they have completed use of the decision aid (~2-4 weeks) during which the pertinent decision aid will be reviewed. Supportive persons identified by the parent or youth will be encouraged to view and use the decision aids along with the enrolled adolescent or parent. The DE will assist participants in identifying any remaining uncertainties they may have about the decision and coaching about how to bring these issues to a clinic visit with the referring HCP. A written summary of the patient's and parent's perspectives during the SMDM sessions, agreement between their perspectives and their remaining issues will be drafted by the DE and forwarded to the referring HCP (See Appendix) and to the research team as an SMDM process measure for each family. The SMDM intervention will conclude with a clinic visit with the referring HCP who will discuss the participants' remaining questions and perspectives about the information they have received and help them to arrive at a consensus decision about the medical option under consideration, including the possibility of deferring the decision to a later date. Those patients who become candidates for more than one of the options of interest during the study will repeat these interactions for each decision being considered

Practical considerations: The process of becoming a candidate for either CSII or CGM may be complicated in several ways that may make it more difficult to evaluate the specific contributions of the SMDM intervention that is planned. Below, we have listed specific complicating factors that can be anticipated and planned methods for addressing each of them:

Complicating Issue	Planned Resolution
Delay between decision to accept CSII or CGM and its actual receipt by the patient and family due to insurance denials, etc.	Questionnaire administration will occur as outlined in the measurement schedule, but collection of CSII or CGM download data will not commence until the device is received and activated.

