Hypothesis 2: Compared to UCP, the SMDM group will have significantly more favorable status in terms of scores for treatment adherence (DSMP-SR), HbA_{1c}, and frequency of moderately severe or severe hypoglycemia at each follow-up measurement point.

Hypothesis 3: Effects of SMDM on indices of optimal use of, and satisfaction with, CSII or CGM will be mediated by changes in the measures of decision quality (Test of CSII or CGM Knowledge, Decision RegretScale, SURE Test, Decision Satisfaction Scale).

Hypothesis 4: Significant moderators of benefit from SMDM along the measured outcomes will include baseline measures of socioeconomic status, health literacy and numeracy, youth age, and family structure.

Hypothesis 5: SMDM will have indistinguishable beneficial effects on the primary study outcomes regardless of which clinical decision (CSII or CGM) was the focus of the SMDM intervention.

Statistical Power Statistical power to detect treatment effects of interest on the primary endpoints was assessed using the online DSS Research Statistical Power Calculator.¹⁷⁴ With enrollment of 166 eligible youth and parents and attrition of 10% over the 12-month study, and a resulting “Completer” sample size of 150, the study will have statistical power of .87 to detect a moderate treatment effect of ~0.4 SD on the measures of decision quality and CSII or CGM optimal use. Even though statistical power remains adequate for detection of somewhat smaller treatment effects, effects of less magnitude are unlikely to have sufficient clinical significance to warrant the added cost and inconvenience of implementing SMDM.

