A subcontract has been negotiated with Thomas Jefferson University that will cover the personnel costs (salary plus fringe benefits) for the involvement of [name]. as a co-investigator on this project. [name] would be supported for 0.6 calendar months (5% FTE) during all 3 project years. Her base salary is above the PCORI cap and is budgeted at \$200,000 annually. Fringe benefits and indirect costs are calculated per established Thomas Jefferson University policies and procedures in effect at the time of this application. The TJU indirect cost rate for such arrangements is below the 40% allowed by PCORI. This subcontract will end on December 31, 2014 as [name] and the research staff at TJU will become Nemours employees at that time.

We are establishing a subcontract with The Barbara Davis Center for Childhood Diabetes, the only freestanding pediatric diabetes treatment center in the US. Affiliated with the University of Colorado College of Medicine and Children's Hospital of Colorado, BDC manages over 3,300 pediatric patients with type 1 diabetes. A subcontract with the Barbara Davis Center would commit BDC to the recruitment of 80 eligible patients/parents between June 1 and November 30, 2015 and to maintain study follow-up over the following 12 months for each participant. The subcontract would cover the personnel costs (salary plus fringe benefits) for the involvement of [name]. as a co-investigator on this project, [name] CDE as Diabetes Nurse and [name] as Research Assistant.

Project Plan And Timeline

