amount of \$500 per adolescent-parent dyad annually to cover their expenses for participation as FAC members. The group will select its own leadership and the elected chairperson will prepare the meeting agenda and conduct the meetings. Minutes will be distributed to all members. The FAC will serve in an advisory capacity to [name] and other members of the research team. The FAC will meet monthly throughout the conduct of the study and will provide input to the research team at each stage of the study, including planning, design, implementation, analysis and dissemination. They will also serve, along with [name], [name] and one of the endocrinologists as the data quality and safety review group for the study and they will process any unanticipated problems such as threats to participants' confidentiality, participant complaints, and other such issues as may arise.

REPLICATION AND REPRODUCIBILITY OF RESEARCH

Replication of Research Findings

This research is structured as a multi-site study that will recruit and randomize patients at four different Nemours pediatric care facilities. While the sites share many features in common since they are all operating entities of the Nemours Foundation, the sites differ in many important respects as well, including geography, demographic characteristics of the respective patient populations, urban versus rural population distribution, and some differences in practice patterns (e.g., proportionately fewer CSII patients in Orlando compared with the other sites; more use of private CSII educators in the Delaware Valley than at the Florida sites). This situation positions us to evaluate the extent to which results obtained from this research hold up consistently across the Nemours enterprise or if successful SMDM appears to depend on specific characteristics of individual T1D clinicians.

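### Site is the stratification factor and educators deliver part of SMDM in one arm only, yet B.5 specifies neither site nor educator in any model, so the standard error can be wrong in either direction and no cross-site analysis is prespecified

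*Combined protocol and SAP*

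**What the plan says.** **Analysis.** Section B.5 (Data Management and Statistical Analysis Plans) states: "Data from all clinics will be pooled for the analyses". The hypotheses are to be tested with mixed or multilevel models, but the levels and random effects are not listed. Site, educator and clinician are not among the candidate moderators. The Statistical Power paragraph makes no allowance for clustering.

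**Randomization.** B.1 (Randomization Procedures) and B.2 (Study Design) use a separate list for each enrolling site, with equal allocation.

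**Delivery.** The SMDM text in B.2 says: "A Diabetes Educator (DE) at each Nemours site and the Barbara Davis Center will conduct face to face interactions with SMDM participants". The educator reviews the decision aid with the family, coaches them and writes a summary for the treating provider. The control arm has no matching study role.

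**Concentration.** Under Part D (Consortium/Contractual Arrangements), a subcontract "would commit BDC to the recruitment of 80 eligible patients/parents between June 1 and November 30, 2015". That subcontract lists one certified diabetes educator, as Diabetes Nurse.

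**Consistency.** Part D (Replication of Research Findings) says that recruiting at four Nemours facilities "positions us to evaluate the extent to which results obtained from this research hold up consistently across the Nemours enterprise". It also raises whether success depends on individual clinicians. B.5 has no matching analysis, only a general allowance for exploratory subgroup work as needed.

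**The concern.** Two features of the design bear on the standard error of the treatment effect, and they pull in opposite directions.

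- **Site differences shared by both arms.** Stratified randomization balances these between arms. A model without site leaves them in the residual, so the standard error is too large and the test loses power.
- **Educator differences in the SMDM arm only.** These make outcomes of families seen by the same educator alike in one arm and not in the other (a partially nested design). A model without an educator or arm-by-site term leaves that variance out, so the standard error is too small.

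Nearly half of the SMDM arm would come from one center. If one educator serves it, a particularly good or poor educator there would move the overall estimate without the interval showing it. A reader could not tell whether the result reflects SMDM in general or one center, because no by-site analysis is fixed in advance.

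**Working it through.** **1. The plan's own figure.** No figure in the plan bears directly on clustering. The nearest is the power statement: "statistical power of .87 to detect a moderate treatment effect of ~0.4 SD", after "attrition of 10% over the 12-month study". The test is two-sided at 0.05 with 150 completers, taken as 75 per arm.

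- Power = Φ(0.4 × √(75/2) − 1.96) = Φ(2.449 − 1.96) = 0.69.
- The stated 0.87 is not reproduced. An effect of 0.5 SD gives Φ(3.062 − 1.96) = 0.86.

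This is a separate matter. Here 0.69 serves only as the baseline without clustering.

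**2. Concentration.** 80/166 = 48%. With equal allocation within site, 80/2 = 40 of 166/2 = 83 SMDM families.

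**3. Educator variance alone.** Assumptions: one educator per site, four Nemours sites plus Denver, and SMDM families split 40 + 4 × 10.75 = 83. The intraclass correlation (ICC) is not in the documents, so a range is shown.

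- Size-weighted mean cluster = (40² + 4 × 10.75²)/83 = 2062.25/83 = 24.85.
- SMDM design effect = 1 + (24.85 − 1) × ICC.
- Variance ratio of the arm difference = (1 + design effect)/2, because the control arm is not clustered.
- True type I error = 2 × [1 − Φ(1.96/√ratio)].

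| ICC | Design effect | Variance ratio | SE understated by | Type I error |
|---|---|---|---|---|
| 0.01 | 1.24 | 1.12 | 5% | 0.064 |
| 0.02 | 1.48 | 1.24 | 10% | 0.078 |
| 0.05 | 2.19 | 1.60 | 21% | 0.121 |

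Five Nemours sites instead of four gives 0.063, 0.077 and 0.118. With the same ratios and 75 completers per arm, power at 0.4 SD falls from 0.69 to 0.64, 0.60 and 0.49, before any loss of degrees of freedom.

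**4. Site and educator variance together.** 20,000 simulated null trials per setting. Each arm has 75 families split 36, 10, 10, 10, 9 over five sites. Variances are shares of the total. Entries are type I error at nominal 0.05.

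| Site variance | Educator variance | Pooled test, no site | Site as fixed factor |
|---|---|---|---|
| 0 | 0 | 0.051 | 0.051 |
| 5% | 0 | 0.045 | 0.049 |
| 10% | 0 | 0.039 | 0.047 |
| 20% | 0 | 0.034 | 0.050 |
| 0 | 1% | 0.062 | 0.063 |
| 0 | 2% | 0.074 | 0.075 |
| 0 | 5% | 0.116 | 0.118 |
| 20% | 1% | 0.050 | 0.069 |
| 20% | 5% | 0.106 | 0.139 |

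The table shows three things:

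- Pooling without site is conservative when only sites differ.
- Pooling is liberal when only educators differ. With both, the errors can cancel by accident (0.050 at 20% and 1%).
- Adding site cures the first error but not the second.

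**5. What a fully protected test costs.** A t-test on the five site-level differences held its level in every setting run (0.044 to 0.049). It has 4 degrees of freedom and a critical value of 2.78 against 1.96, a factor of 1.42.

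**The case against.** A reader might infer that one educator per site delivers SMDM, that the plan ignores this, and that p-values are therefore too small. The documents do not support that much.

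- **Number of educators.** The B.2 sentence is singular, but the Abstract and the budget justification speak of educators, in the plural, at each site. If two educators shared Denver equally (20 + 20 + 4 × 10.75), the type I errors in step 3 would fall to 0.058, 0.067 and 0.092.
- **Not every SMDM family is nested.** Under Recruitment Plan C, remote families get no educator summary. Their number is not given.
- **The 80 families are a target.** Their recruitment window also runs past the 6/30/15 close of enrollment given in B.1.
- **The ICC may be small.** The core of SMDM is a standard web tool, and B.6 describes the educator's part as structured and time-limited. Usual-practice families also receive education at the same sites, so some educator influence may be common to both arms.
- **The direction is not fixed.** Omitting shared site differences works the other way, as step 4 shows.
- **Pooling may mean only combining data.** A multilevel model with unstated levels does not exclude a site or educator term.
- **Part D makes no firm promise.** It says what the design makes possible, and only for Nemours sites.

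All of this stands, and it limits the claim to under-specification with an uncertain direction. It does not supply the missing model terms. An accidental balance of two omissions is not a reason to leave both in place.

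**Conclusion.** The point holds as a gap in specification. B.5 does not name the factor by which the trial randomizes, does not address educator clustering in the SMDM arm, and fixes no analysis for the cross-site question that Part D raises.

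Depending on which variance dominates, the pooled test's type I error would lie at about 0.03 to 0.045 (site variance 5% to 20%, no educator variance) or about 0.06 to 0.12 (educator ICC 0.01 to 0.05, no site variance). These figures assume one educator per site, about five sites and Denver at 48% of the sample. Both variance ranges are assumptions, because the documents give none.

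The claim that p-values are too small would need an educator ICC that is known and large relative to site variance. With one educator per site, an educator effect also cannot be separated from a site-by-arm interaction. A random term on about five very unequal clusters is therefore suitable as a sensitivity analysis, not as the primary model.

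**What to change.** In B.5:

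1. Include enrolling site as a factor in every Hypothesis 1 and Hypothesis 2 model, and say how remotely recruited families are assigned to a site stratum.
2. As prespecified sensitivity analyses, report the SMDM effect by site, and overall with and without the Barbara Davis Center. Also fit a model with an arm-by-site (educator) term and small-sample degrees of freedom such as Kenward-Roger.
3. Record which educator, if any, saw each SMDM family. The clinic identifier already planned for the dataset is not enough if a site has more than one educator.
4. In Part D (Replication of Research Findings), refer to these analyses and say whether the Barbara Davis Center is covered.

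The cost is SAP wording, one data field and some analysis work, with no change to design or sample size. Adding site to the main models costs a few degrees of freedom. It also removes the accidental offset in step 4, so the sensitivity model must be reported beside it. The sensitivity intervals will be clearly wider (by about 1.4 from the critical value alone at 4 degrees of freedom) and imprecise with about five sites.
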